We will randomly assign participants to either the IMPACT intervention of usual care (UC) prior to their first intervention point. [name] (lead statistician) will develop a random allocation scheme by considering stratification to form blocks with respect to important determinants such as ethnicity, gender, etc. Within each stratum or block, we will accomplish random allocation to IMPACT vs UC with systematic sampling (e.g. alternating the assignment of IMPACT and UC with a random start). This scheme will result in a nearly equal number of patients in IMPACT and UC within a block. We will reduce potential bias using stratified randomization by preventing potentially inferring treatment allocation *a priori*. It also reduces bias by balanced assignment so that potential determinants of outcomes are comparable across intervention groups. We can also use systematic sampling to reduce sampling variation in comparison with simple random sampling. Because of the close interaction between the clinical team and the research interventionists, we will not be able to blind the clinical team to group assignment.^{50,51} After [name] creates the allocation scheme, he will give it to the research coordinator, who will put the allocation assignments into separate sealed envelopes. The research coordinator will place the master list in a locked file cabinet drawer in the office of the PI's Office Administrator. Only the sequence numbers (A1 – block A patient #1, A2, A3, etc.) will appear on the sealed envelopes and the corresponding group assignment will be placed inside the envelope. The research coordinator will open the sealed envelope sequentially and inform the consented participant of his or her assigned group. After random assignment, the research coordinator will direct participants in the IMPACT intervention to the study interventionists (the physical therapist and dietitian).

4. Inclusion and Exclusion Criteria

We plan to recruit participants shortly before or after undergoing KT at the UNM HSC Transplant Center. The Transplant Center provides transplant services to all New Mexico residents as well as the surrounding Pueblos and the Navajo Nation. Reflecting the demographics of the state, only 3% of patients are AA at UNM. Male and female KT recipients aged 18 and older will be eligible for enrollment.

Transplant Patients

Inclusion criteria:

1. Received kidney transplant at the University of New Mexico
2. Greater than 18 years of age

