PROTOCOL TITLE: **Improving Healthcare Outcomes in American Indian and Hispanic Transplant Recipients Using Culturally-Tailored Novel Technology (IMPACT)**

3. American Indian (AI) or other race, White (WH) or Hispanic/Latina(o) (HL)
4. Mentally competent

Exclusion criteria:

1. Children under the age of 18
2. Incarcerated patients
3. Pregnant women

Team Members

Inclusion criteria:

1. Transplant clinic staff
2. Key administrators involved in the transplant process

5. Number of Subjects

To estimate the number of patients we can expect to recruit for the study, we used data from the last five years of KT recipients at UNM HSC. The center transplants an average of 33 patients per year. For the study, we plan a 12-month recruitment period. Of all eligible patients who receive a KT, we expect that 80% will agree to participate in our study (n=26), based on previous intervention research with KT patients,^{13,16,17,34,41,52-54} and our own work.⁵⁵⁻⁵⁷ Thus, for this pilot trial, we aim to recruit and retain 14-20 KT recipients. Virtually all of UNM ESKD patients are (a) HL (44%) or AI (33%), (b) income <\$25K, (c) on public insurance, (d) high school or lower education; and/or, (e) low occupational status. Thus, our patient sample will include members of different vulnerable populations that have been underrepresented in past research, and hence prepare us to conduct a formal study in a diverse population.

Team members will include up to fifteen people from the following groups: transplant clinic staff and key administrators.

6. Study Timelines

Participant expected duration in the study will be one year, if they complete all study visits. Patient recruitment and enrollment will be completed in 12 months of the study (Month 4, Year 1 through Month 3, Year 2). Participant follow-up, data analysis, and manuscripts are schedule to be completed in Year 2 of the study.

Project Period: 03/01/2020 – 02/28/2022									
Activity	Year: Month:	01		02					
		1-3	4-6	7-9	10-12	1-3	4-6	7-9	10-12
Project Startup (e.g., hiring and training staff; database creation)		----							
Participant Recruitment		-----		---					

PROTOCOL TITLE: **Improving Healthcare Outcomes in American Indian and Hispanic Transplant Recipients Using Culturally-Tailored Novel Technology (IMPACT)**

Participant Follow-up		
Team Member Surveys		
Data Quality Evaluation and Observation Logging	-----	-----
Data Analysis		-----
Present Initial Findings at Conferences		---

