Surveys with clinical team and administrators: We will create a provisional codebook with the barriers and facilitators we identified in the brief surveys with key stakeholders. We will pay particular attention to themes that deal with overall ease of use of the intervention and overall satisfaction with implementation.

14. Provisions to Monitor the Data to Ensure the Safety of Subjects

PROTOCOL TITLE: Improving Healthcare Outcomes in American Indian and Hispanic Transplant Recipients Using Culturally-Tailored Novel Technology (IMPACT)

A DSMB will be created to oversee this study. DSMB members will be composed of the Principal Investigator and Co-Investigators with expertise in kidney transplantation, clinical trials, disparities, and biostatistics, plus one independent reviewer (IR), who has no financial, scientific, or other conflict of interest with the study. Written documentation for the IR attesting to absence of conflict of interest will be required. The study team will present the IR with the study protocol, informed consents, and reports to assess study safety and progress. In addition, the co-investigators will explain plans for participant recruitment, accrual and retention, participant risk versus benefit, performance of the trial sites, confidentiality of patient data, monitoring of study progress and assessment of other factors that can affect study outcome during the DSMB meeting.

The IR will review all data captured for the study including unanticipated events. This will allow the Principal Investigator and study team to assess whether more frequent monitoring will need to take place and how it will affect others currently enrolled. The IR will have the authority to recommend stopping the study early or modifying the study design for safety concerns. The DSMB will review the progress of the study within 2 weeks after the first patient is randomized into the study and will conduct meetings routinely thereafter until enrollment is closed. The IR will recommend terminating the study if the safety, welfare and health of patients is jeopardized due to conducting the study according to protocol. Unanticipated events will be reported by the study team to the IR and the IRB within 24 hours of becoming aware of the event. The Principal Investigator will assess the adverse event (AE)/serious adverse event (SAE) relationship to the IMPACT intervention.

15. Withdrawal of Subjects

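### Routine DSMB meetings end when enrolment closes, although the last participants then have 9 to 12 months still to run, some of it in the intervention

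*Combined protocol and SAP*

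**What the plan says.** Section 14 of the combined protocol and SAP sets a first DSMB review within two weeks of the first randomisation. After that the board "will conduct meetings routinely thereafter until enrollment is closed". No interval is given for the routine meetings, and no meeting or closing review after enrolment is stated elsewhere.

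The board consists of the Principal Investigator, co-investigators and one independent reviewer. Section 14 says of that reviewer: "The IR will review all data captured for the study including unanticipated events", and "The IR will have the authority to recommend stopping the study early or modifying the study design for safety concerns". It places the discussion of recruitment, risk versus benefit and study progress at the DSMB meeting.

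Section 6 supplies the calendar. On enrolment: "Patient recruitment and enrollment will be completed in 12 months of the study (Month 4, Year 1 through Month 3, Year 2". On each person: "Participant expected duration in the study will be one year, if they complete all study visits". On the end of the study: "Participant follow-up, data analysis, and manuscripts are schedule to be completed in Year 2 of the study".

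Section 12 has the exercise intervention begin at surgical clearance, usually 6-8 weeks after transplant, delivered at clinic visits that it lists to month 6. The dietitian sees IMPACT participants through six months, with a follow-up at 12 months.

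**The concern.** The meeting schedule is tied to recruitment, but participants are exposed to the intervention after recruitment. When the last person is enrolled, that person has not yet begun exercise, and others are partway through. A meeting schedule that stops there leaves the later part of the intervention, and nearly all of the second half-year for late enrolees, without a routine board review.

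At stake is the collective look. Event-by-event reporting catches a single unanticipated event. A pattern visible only across participants is more naturally seen when the accumulated data are laid out together. The independent reviewer is the only board member who is not an investigator on the study, so the routine meeting matters most for that role. The reviewer's power to recommend stopping or modifying the study still has a use while people remain in the intervention.

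**Working it through.** **Calendar, from stated dates only**
- Enrolment runs from project month 4 to month 15: 15 - 4 + 1 = 12 months, which reproduces the plan's 12.
- One full year for a participant enrolled at the end of month 15 ends at month 15 + 12 = 27, which is 12 months after closure.
- If follow-up is completed in Year 2, it ends at month 24: 24 - 15 = 9 months after closure.
- So the last participant has 9 to 12 months after routine meetings end. The two ends of the range reflect two Section 6 statements that do not agree for late enrolees.

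**Exercise-phase time after closure (assumptions needed)**
- Arm size: Section 3 says "This scheme will result in a nearly equal number of patients in IMPACT and UC within a block". Half of 14-20 is 7-10 people in IMPACT.
- Start *s*: 6-8 weeks = 42/30.44 to 56/30.44 = 1.38 to 1.84 months after transplant.
- End *e*: month 6. This is assumed from the visit schedule; the text states no end and Figure 2 is not shown.
- Entry at transplant, uniform over an enrolment window of *A* months. Also assumed.
- The last meeting is taken to fall at closure. With no stated interval it could be earlier, which would make the shares larger.

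For a person entering at time *t*, exercise time after closure is max(0, min(*e* - *s*, *t* + *e* - *A*)). Averaged over uniform entry with *A* ≥ *e*, this is (*e*² - *s*²)/(2*A*). Divided by the phase length *e* - *s*, the share is (*e* + *s*)/(2*A*).

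| Case | Share after closure |
|---|---|
| *A* = 12, *e* = 6 | 7.38/24 to 7.84/24 = 30.7% to 32.7% |
| *A* = 12, *e* = 5 | 6.38/24 to 6.84/24 = 26.6% to 28.5% |
| *A* = 12, *e* = 6, entry density falling linearly to zero | 10.7% to 11.7% |
| *A* = 12, *e* = 6, entry density rising linearly from zero | 50.8% to 53.7% |

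Person-months for *A* = 12, *e* = 6: (36 - *s*²)/24 = 1.36 to 1.42 months per person. Times 7 gives 9.5 to 9.9; times 10 gives 13.6 to 14.2. Hence roughly 10-14.

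The chance of starting exercise after closure is *s*/12 = 11.5% to 15.3%. In 7-10 people that is 0.8 to 1.5, or about one person.

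**If enrolment closes on reaching target**
- Section 5 expects 33 × 0.80 = 26.4 consenting per year (the plan's n = 26), or 2.2 per month. Reaching 14 takes 14/2.2 = 6.4 months; reaching 20 takes 20/2.2 = 9.1 months.
- Exercise share (6 + *s*)/(2*A*): 58% to 62% at *A* = 6.4, and 41% to 43% at *A* = 9.1.
- All follow-up time, both arms, 1 - *A*/24: 73% and 62%. The corresponding figure for a 12-month window is 50%.

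**The case against.** The best answer is that safety oversight continues, and that stands. A reader might infer from Section 14 that nobody watches the trial once enrolment closes. The documents do not support this. Unanticipated events go to the independent reviewer and the IRB within 24 hours. The reviewer's examination of all captured data and authority to recommend stopping carry no link to enrolment. Section 14 adds: "This will allow the Principal Investigator and study team to assess whether more frequent monitoring will need to take place". Usual care keeps monthly clinic visits to month 12 (Section 12), the coordinator's log is reviewed at standing team meetings (Section 12), platform alerts are monitored (Section 3), and the dietitian and physical therapist monitor participants (Section 18). These do not replace the routine meeting: the event reporting is case by case, the data review has no stated frequency, and the rest is done by the clinical or study team.

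Second, a reader might say the defect is that reviews lose their dates at closure. That also fails. Only the first meeting has a date; during enrolment the others are merely routine. The contrast is between routine meetings and none.

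Third, the large pooled figures can mislead. Every 12-month visit, and about half of all follow-up time under 12-month uniform accrual, falls after closure. But this counts usual care, which receives no study intervention, and months 6-12, when the only dietitian contact listed for IMPACT is the 12-month follow-up. It does not measure intervention exposure.

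Fourth, ending meetings at the last participant's month 6 might be enough. That is arguable, but it relies on an end of the exercise phase that the text does not state.

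**Conclusion.** The point holds in a limited form. Section 14 sets a stopping rule for routine DSMB meetings that comes too early for the follow-up the plan describes. The 9 to 12 months left for the last participant rest on stated dates alone. The 31%-33% of exercise-phase time, roughly 10-14 person-months in 7-10 people, rests on uniform accrual over 12 months, entry at transplant and a month-6 end of exercise. Varying the accrual shape moves the share from about 11% to 54%, and early closure at target raises the uniform figure to 41%-62%.

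What lapses is the routine forum for the independent member, not oversight as a whole. With one site, 14-20 people and intervention risk described as minimal, importance is modest. The change is still worth making because it is so small.

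**What to change.** In Section 14, change the end point of the routine meetings from the close of enrolment to the last participant's completion of the last study visit. State the meeting interval in the same sentence; without it, the extension alone would not schedule the later reviews.

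The cost is one sentence and a few short meetings of existing members. If the interval were quarterly (an assumption, since the plan gives none), that is 9/3 = 3 extra meetings if follow-up ends in Year 2, or 12/3 = 4 if every participant completes a full year. Stopping instead at the last participant's month 6 would need 6/3 = 2, so running to the last visit costs one or two more and avoids relying on an unstated end of the exercise phase. No endpoint, visit or study procedure for participants changes.

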34. Principal Investigator's Assurance	22
35. CHECKLIST SECTION.....	24
36. Partial Waiver of Consent for Screening/Recruitment.....	24
37. Partial Waiver of HIPAA Authorization for Screening/Recruitment.....	25
38. Waiver of Documentation of Consent	25
39. Alteration of Consent.....	26
40. Full Waiver of Consent/Parental Permission	27
41. Full Waiver of Consent/Parental Permission (Public Benefit or Service Programs)	28
42. Full Waiver of HIPAA Authorization (Checklist)	28
43. Other Waiver Types (Checklist).....	29

PROTOCOL TITLE: **Improving Healthcare Outcomes in American Indian and Hispanic Transplant Recipients Using Culturally-Tailored Novel Technology (IMPACT)**

44. Vulnerable Populations (Checklist).....	29
45. Medical Devices (Checklist).....	35
46. Export Control (Checklist)	36
47. Data Transfer/Sharing (Checklist)	36
48. Specimen Transfer/Sharing (Checklist).....	37

PROTOCOL TITLE: **Improving Healthcare Outcomes in American Indian and Hispanic Transplant Recipients Using Culturally-Tailored Novel Technology (IMPACT)**

1. Objectives

Aim 1: Examine IMPACT's acceptability and feasibility in AI and HL KT recipients.

1a. We will assess acceptability by patient ratings of satisfaction with the culturally-tailored diet and exercise intervention, as well as the Twistle patient engagement platform.

1b. We will assess feasibility by determining recruitment and retention rates and assessing participant adherence to the IMPACT intervention.

1c. We will determine the ideal personnel hours and number of staff required for the physical therapist/exercise physiologist and registered dietitian nutritionist roles.

Aim 2: Test the efficacy of IMPACT on proximal outcomes (e.g., weight, lipid profile, HbA1c, sleep quality, QOL) and distal outcomes (e.g., occupational functioning) in kidney transplant recipients.

2a. We will assess participants' adherence to the exercise and diet intervention aspects of IMPACT.

2b. We will begin to examine the relationship between adherence to IMPACT and patient outcomes.

2. Background

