Report and Manuscript Preparation		---

7. Study Endpoints

The primary endpoints for the pilot trial are intervention **acceptability** and **feasibility**. To assess **intervention acceptability** we will measure patients' satisfaction with the interventions with a revised version of the Client Satisfaction Questionnaire,⁵⁸⁻⁶⁰ where higher satisfaction will indicate greater intervention acceptability, and the System Usability Scale (SUS),⁶¹ where higher scores indicate ease of usability. We will assess questionnaire acceptability using open-ended patient questions. In addition to quantifying **feasibility** using **recruitment and retention rates**, to provide concrete estimates of the expected rates of missing data and participant attrition, we will keep a detailed log of relevant factors that could create barriers to subsequent study completion. We will measure time spent sedentary (sitting/lying), standing, and stepping (and the intensity) during awake hours with the activPAL3 accelerometers, and compare these values between the IMPACT and UC groups. Time required for study participation will be measured using survey completion times as well as intervention session time estimates.

In addition to the primary endpoints noted above, we will assess the feasibility and acceptability of collecting a number of patient outcomes that will be the key target outcomes in a large scale R01. A systematic review of 35 randomized controlled trials of exercise training in solid organ transplant recipients, including 9 kidney, 21 heart, 3 lung, and 2 liver transplant studies, found that there were a total of 62 patient outcome measures, including peak VO₂, SF-36 score, and muscle strength.⁵² Of these, our team determined that the most relevant outcomes to assess in our pilot include: (a) variables that we will gather from participants' medical records (i.e., % weight change, lipid profile, and HbA1c); (b) patient reported outcomes, including the PROMIS Sleep Related Impairment⁶² and Sleep Disturbance⁶³ Measures and PROMIS Global Health⁶⁴; and, (c) occupational functioning, using the occupation subscale of the CHART-SF.⁶⁵ The CHART-SF is the most widely used participation measure in rehabilitation research,⁶⁶ and has been used in various ethnic groups.⁶⁷

8. Research Setting

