Intervention timing: We will minimize participant burden by applying the interventions during patients' standard post-transplant clinic visits. We display how the intervention time points correspond to the standard clinic schedule in Figure 2. The transplant team schedules patients for appointments at the post-transplant clinic 1x/week for the first month, then every two weeks for the next two months, then once a month at 4-6 months post-KT. Surgical clearance usually occurs 6-8 weeks post-KT, at which point the exercise intervention can begin. We will take advantage of these frequent in-person visits to deploy our exercise and diet intervention. Prior to the start of the exercise intervention, we will include a "baseline" test. We will measure time spent sedentary (sitting/lying), standing, and stepping (and the intensity) during awake hours with the activPAL3 accelerometers. At the baseline visit for both groups, we will assess self-reported exercise and physical functioning prior to transplant. Those in usual care will not undergo any diet or exercise intervention, but will wear an activity monitor. They will only undergo the baseline interview, and a follow-up at 6 and 12-months post-transplant. We will repeat the objective assessment of sedentary and physical activities at the 6 and 12-month follow-ups for all participants.

Participants in either arm may have delayed activPal monitor assessments at any of the four timepoints, based on current health status and at the discretion of the PI.

Figure 2. IMPACT and UC Participant Pathway

Exercise intervention: Patient-reported levels of physical activity and objective measures of physical fitness indicate lower levels of exercise in ESKD patients awaiting KT. After KT, physical activity increases, but it remains lower than in the general population.¹²²⁻¹²⁵ Based on the most recent meta-analyses/reviews of physical activity post-transplant,^{33,126,127} our approach combines instructions that are professionally-assessed with the culturally-tailored assessment of exercise needs (Appendix A), guided by a therapist, and incorporate a rehabilitation approach to slowly increasing KT recipients' physical activity⁴⁰⁻⁴² with appropriate build-up to more intense physical activity until they can engage in KDOQI guideline-based exercise.¹²⁸ After the initial

PROTOCOL TITLE: **Improving Healthcare Outcomes in American Indian and Hispanic Transplant Recipients Using Culturally-Tailored Novel Technology (IMPACT)**

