 - a. PROMIS Global Health Measures
 - b. PROMIS Sleep Related Impairment and Sleep Disturbance Measures
 - c. Satisfaction with Intervention
 - d. Usability Scale for Twistle Platform
 - e. Occupational functioning
2. Medical records
 - a. % weight change
 - b. Lipid profile
 - c. HbA1c

Predictors and Covariates

1. Questionnaires
 - a. Demographics
 - b. Sense of Mastery
 - c. Social Support
 - d. Kinesiophobia
 - e. Diet and exercise adherence
2. Medical records
 - a. Immunosuppression protocol
 - b. BMI
 - c. Other transplant relevant medical history

13. Data Analysis

Intervention Evaluation

We will evaluate the process of implementing the IMPACT intervention using a mixed-methods approach consistent with a Type I Hybrid Intervention/Implementation design.¹³⁰ Using the Consolidated Framework for Implementation Research (CFIR)¹³¹ as a theoretical framework, we will assess barriers and facilitators to implementation to provide real-time feedback for the pilot and to inform the future large-scale project. This evaluation will be comprised of a periodic survey of research, clinical, and administrative staff regarding barriers and facilitators of implementation and in-depth interviews with participants regarding experiences with the interventions.

Quantitative Analysis Plan

Primary and ancillary analysis: We will describe our patient sample with detailed descriptive statistics with respect to demographics and health-related characteristics. We

PROTOCOL TITLE: Improving Healthcare Outcomes in American Indian and Hispanic Transplant Recipients Using Culturally-Tailored Novel Technology (IMPACT)

will record and summarize missing data points during the study, attrition and its underlying reasons when feasible. Our primary analysis will focus on measures of feasibility and acceptability as outlined in Aim 1: Examine IMPACT's acceptability and feasibility in an ethnically diverse KT recipient population. We will use these analyses to determine endpoints, their variation, plausible intervention effect size, sample size, planned analyses, and accrual expectations. These analyses will guide the design of the subsequent study.¹³² We will also use these analyses, as well as those of Aim 2 to determine a clear rationale to support the next steps in the study process, including “go versus no go” decisions.¹³²

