Subjects are free to withdraw from study participation at any time during this clinical study. The Investigator may withdraw a subject if continued participation is not in the interest of the subject's health and welfare, for noncompliance with protocol-specified procedures, or because of a protocol violation. This will be evaluated on a case-by-case basis by the Investigator. All data collected from a withdrawn participant will be destroyed if the participant withdraws from the study at any point.

The primary reason for discontinuation or withdrawal will be documented as one of the following:

- Adverse Event
- Noncompliance
- Protocol violation

16. Data Management/Confidentiality

The PI will oversee all aspects of data management in close collaboration with the lead study statistician, [name]. The study team will work with the Twistle, Inc. team to develop an operations manual to standardize all procedures and staff training in areas such as patient recruitment, measurement, assessment, and data entry, management, and security. Following the guidelines outlined in the operations manual the statistical team will create an electronic data entry system using REDCap,

PROTOCOL TITLE: Improving Healthcare Outcomes in American Indian and Hispanic Transplant Recipients Using Culturally-Tailored Novel Technology (IMPACT)

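### The investigator may withdraw participants for noncompliance, mainly in the IMPACT arm, in a pilot whose feasibility endpoint is measured by retention and adherence

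*Combined protocol and SAP*

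**What the plan says.** **Withdrawal (Section 15).** Besides withdrawal for health and welfare, the investigator may withdraw a subject "for noncompliance with protocol-specified procedures, or because of a protocol violation". No threshold is given: "This will be evaluated on a case-by-case basis by the Investigator". The section does not distinguish stopping the intervention from leaving the study. It adds: "All data collected from a withdrawn participant will be destroyed if the participant withdraws from the study at any point".

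**Reasons (Section 15).** "The primary reason for discontinuation or withdrawal will be documented as one of the following": adverse event, noncompliance or protocol violation. The same section says that subjects may leave whenever they wish.

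**Endpoints.** Section 7 begins "The primary endpoints for the pilot trial are intervention" acceptability and feasibility, and quantifies feasibility by recruitment and retention rates. Aim 1b in Section 1 adds adherence: "We will assess feasibility by determining recruitment and retention rates and assessing participant adherence to the IMPACT intervention". Aim 2a assesses adherence to diet and exercise, and Aim 2b relates adherence to outcomes. Under Section 13 the primary analysis "will focus on measures of feasibility and acceptability as outlined in Aim 1", and attrition and its reasons are to be summarised when feasible.

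**Burden by arm.** Section 23 pays for three visits in usual care and thirteen in IMPACT. Section 12 gives usual care no diet or exercise intervention: "They will only undergo the baseline interview, and a follow-up at 6 and 12-months post-transplant". Usual care participants do wear the activity monitor, and Section 12 refers to four monitor time points in either arm. Section 23 places the IMPACT in-depth interview at the last follow-up visit.

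**The concern.** In most trials a noncompliance clause is routine. Here noncompliance is part of what is being measured. A participant who stops exercising or misses visits is a feasibility result. If that person is withdrawn, poor adherence is turned into attrition by a staff decision, and no blinding of the person deciding is described.

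Three things are at stake. Retention becomes partly the investigator's own act. The 6- and 12-month assessments and the final interview are lost for the people who could say most about barriers, and the low end of the adherence range that Aim 2b needs is thinned. Adherence may be reported only for those who remain. Section 13 uses these results to plan the next study and to decide whether to go ahead with it.

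The closed reason list adds a separate problem. Someone who leaves by choice or is lost to follow-up has no matching code.

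**Working it through.** **Inputs from the protocol.** Target of 14-20 participants (Section 5) with near-equal allocation (Section 3), so about 7-10 per arm. Visits: 13 in IMPACT and 3 in usual care (Section 23). Four monitor wears in either arm (Section 12).

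**Not given, so assumed.** The miss rate per contact (q), the number of non-adherers in IMPACT (b = 2 to 4) and the number removed (r = 1 or 2).

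**The plan's own figure.** 33 transplants a year × 0.80 agreement = 26.4, which agrees with the 26 in Section 5. Nothing below depends on it.

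**Step 1: which arm is more exposed?** The chance of at least one missed contact among k is 1 − (1 − q)^k. The IMPACT share is the IMPACT chance divided by the sum of both, for equal arms.

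| q | Usual care, k=3 | IMPACT, k=13 | IMPACT share | Usual care with wears, k=7 | IMPACT with wears, k=17 | IMPACT share |
|---|---|---|---|---|---|---|
| 2% | 5.9% | 23.1% | 79.7% | 13.2% | 29.1% | 68.8% |
| 5% | 14.3% | 48.7% | 77.3% | 30.2% | 58.2% | 65.9% |
| 10% | 27.1% | 74.6% | 73.3% | 52.2% | 83.3% | 61.5% |
| 20% | 48.8% | 94.5% | 65.9% | 79.0% | 97.7% | 55.3% |

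A missed contact is not the same as noncompliance, so this shows relative opportunity only. Failure to follow the diet or exercise plan is not in the table and can arise only in IMPACT.

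**Step 2: retention.** Removing one person who would otherwise have stayed lowers retention among all randomised to that arm by 1/n: 1/10 = 10 points, or 1/7 = 14 points.

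**Step 3: adherence.** With everyone randomised in the denominator, the adherent proportion is (n − b)/n. If r non-adherers leave the denominator, it is (n − b)/(n − r).

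| n | b | All randomised | r = 1 | r = 2 |
|---|---|---|---|---|
| 10 | 2 | 80.0% | 88.9% (+8.9) | 100% (+20.0) |
| 10 | 3 | 70.0% | 77.8% (+7.8) | 87.5% (+17.5) |
| 10 | 4 | 60.0% | 66.7% (+6.7) | 75.0% (+15.0) |
| 7 | 2 | 71.4% | 83.3% (+11.9) | 100% (+28.6) |
| 7 | 3 | 57.1% | 66.7% (+9.5) | 80.0% (+22.9) |
| 7 | 4 | 42.9% | 50.0% (+7.1) | 60.0% (+17.1) |

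The rise is about 7 to 29 points. If the removed participants stay in the denominator as non-adherent, the rise is zero.

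Mean attendance behaves in the same way. Suppose 7 participants attend 90% of sessions and 3 attend 20%. The mean is (7 × 0.90 + 3 × 0.20)/10 = 69%. If the three leave the denominator it is 90%. If they are kept and sessions after removal count as missed, it lies between (7 × 0.90 + 3 × 0)/10 = 63% and 69%.

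**Step 4: does the plan settle the denominator?** No section states that all randomised participants are analysed, that non-adherers stay in follow-up, or how investigator withdrawals count in retention. The data-destruction sentence could force exclusion, but it speaks of the participant withdrawing and may not cover withdrawal by the investigator.

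**Step 5: the reason list.** Section 15 allows departure at will, yet each of its three codes describes something else. Section 13 plans to summarise reasons for attrition. This mismatch needs no assumption.

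**The case against.** The clause is permissive, refers to protocol procedures in general, and does not say that low diet or exercise adherence triggers it. Elsewhere the plan leans towards keeping people: Twistle is meant to support retention, monitor wear may be delayed for health reasons, monitors may be mailed, and patients who cannot do an exercise are directed to the therapist. The barrier log in Section 7 and the coordinator's log in Section 12 may record reasons that the code list omits. The trial is a small pilot, and Section 13 does not expect significant differences between arms. All of this stands, and it limits the severity. It does not supply a threshold, a follow-up rule or a denominator.

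A reader might also infer more than the documents support:

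- *That adherence and retention are the primary endpoints.* The named endpoints are acceptability and feasibility. Retention and adherence are measures of feasibility, and adherence enters through Aim 1b.
- *That removals fall almost only on IMPACT.* The rule covers both arms, and usual care has visits, questionnaires and monitor wear that can be missed. Step 1 gives IMPACT shares of about 55% to 80%, so 
 mainly is as far as the documents go.
- *That adherence is inflated whatever happens to the data.* It is inflated only if removed participants leave the denominator. The loss of retention and follow-up does not depend on that.
- *That leavers will be coded as noncompliant.* The list has no right code for them, but which wrong code would be chosen is conjecture.

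**Conclusion.** The concern holds in this form: a discretionary noncompliance rule with no threshold acts on behaviour that the feasibility endpoint is meant to measure, and the plan has no safeguard against it.

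Each removal costs 10 to 14 points of retention in its arm, provided that the person would otherwise have stayed and that retention is counted over all randomised. It also costs the remaining assessments and, in IMPACT, the final interview. The gain of about 7 to 29 points in reported adherence is conditional on exclusion from the denominator and on the assumed numbers of non-adherers and removals. The gap in the reason list is plain from the text.

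This should be fixed. It does not invalidate the pilot, but follow-up that was never collected cannot be recovered later.

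**What to change.** In Section 15:

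1. State that non-adherence to diet, exercise, Twistle or visits is not in itself a ground for removal from follow-up. Such participants stay in their assigned arm and are invited to the 6- and 12-month assessments. Leave unchanged withdrawal for health and welfare, the participant's right to leave, and the handling of anyone found ineligible.
2. Record stopping the intervention and leaving the study as separate events, each with its own date.
3. Add reason codes for participant decision (with a sub-reason), lost to follow-up, graft loss or death, and investigator decision on welfare.
4. Calculate adherence over everyone randomised to IMPACT and retention over everyone randomised, and report investigator withdrawals separately. For this to work, the section must also say whether the data-destruction sentence applies to withdrawals made by the investigator.

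The cost is protocol wording and a few REDCap codes. The small downside is that staff continue to contact a few disengaged participants.
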